#### **Adverse Events resulting in treatment discontinuation**

TEAEs are derived as resulting in treatment discontinuation if the “Action taken with Study Treatment” is recorded as “Drug Withdrawn”.

#### **Adverse Events related to study treatment**

A TEAE is classified as ‘Related’ to Study Treatment if the relationship to study medication is recorded as ‘Unlikely’, ‘Possible’ or ‘Probable’. A TEAE is classified as unrelated to study medication if the relationship to study medication is recorded as ‘Not Related’. TEAEs with unknown relationship to Study Treatment are counted as ‘Related’ to Study Treatment.

#### **Adverse Events Leading to Death**

A TEAE is derived as leading to death if the outcome is recorded as “Died”.

#### **Adverse Events During COVID-19 treatment interruptions**

For patients with treatment interruptions that result in gaps in dosing of greater than 60 days, adverse events are only considered treatment emergent if they occur within 60 days following the last dose. Adverse events that occurred greater than 60 days following the last dose will not be considered treatment emergent. For this population of patients whose long treatment interruption was due to COVID-19, three types of summarizations will be prepared:

- On dose (treatment emergent) adverse events
- Off dose (not treatment emergent) adverse events. Off dose events are those that occur during a period >60 days following a dose and prior to the immediately following dose.
- Restart (TEAE after restart of treatment) adverse events. Restart events are those that occur on/after the first dose after an off-dose period and prior to the start of any following off dose period.

Times to be considered as treatment interruptions due to Covid-19 are provided by EryDel in form of an excel spreadsheet.

|   |         |  |
|---|---------|--|
| CD+4 Lymphocyte count   | x10E9/L | Month 6 and Month 12   |
| Early morning Plasma Cortisol testing for Adrenal Insufficiency | µg/dL   | As needed: when patients are symptomatic, and when patients are at most risk for adrenal insufficiency and adrenal crisis, such as following discontinuation or interruptions of dexamethasone dosing |
| High dose ACTH stimulation test                                 | µg/dL   | As needed: In the event that patients show signs or symptoms of adrenal insufficiency during the study  |

All laboratory assessments are performed at local laboratories. Quantitative laboratory results are converted to their respective Reporting units for use in summary tables. Assessment of results as being within the normal range are made by the local laboratory. *Any laboratory abnormalities meeting the definition of an adverse event should be recorded on the Adverse Events CRF.*

Clinically notable values of standard laboratory are derived based on SI units as outline in Appendix 13.1.

If repeat tests are performed at any visit the result documented under the nominal visit label is used in all summaries and analyses for that Visit.

Baseline is as described in Section 7.1.

The change from baseline is calculated for quantitative laboratory tests at each scheduled post-baseline visit as:

- Change from baseline = Scheduled Visit result (measured or derived) – Baseline value.

### Special Laboratory: Adrenal Insufficiency Screening

As part of the Special Laboratory evaluations, patients are screened for adrenal insufficiency. The results are recorded on the ‘Screening for Adrenal Insufficiency’ eCRF page.

### Special Laboratory: Early Morning Plasma Cortisol and ACTH Stimulation Test

Patients’ Early Morning Plasma Cortisol levels are recorded on the ‘Early Morning Plasma Cortisol’ eCRF page and ACTH Stimulation Test data are recorded on the ‘ACTH Stimulation Test’ eCRF page.

### Pregnancy Testing

A serum pregnancy test is performed every 6 months and at the Safety follow up visit for women of childbearing potential. A monthly urine pregnancy test is also performed before every infusion throughout the study. Results are recorded on the ‘Serum Pregnancy Test’ or ‘Urine Pregnancy Test’ eCRF pages.

### Culture-based sterility test on EDS-EP

## Process Events

The EDS-EP process is derived as being not fully complete if the response to “Was EDS-EP infusion completed?” is recorded as “No” on the ‘EDS-EP Infusion’ page.

## Vital Signs

*Vital signs assessments are performed pre- and post-infusion at all visits with additional triplicate pre- and post-infusion assessments every 6 months as specified on the Schedule of Visits. Vital Sign assessments include body weight, temperature (oral or tympanic, according to the specific medical practice of the Center), pulse, systolic and diastolic blood pressure, and respiratory rate. Height will be measured by a stadiometer in triplicate at each required visit and used along with body weight (also measured in triplicate at each required visit) to calculate Body Mass Index (BMI). Pulse and blood pressure will be measured after the patient has been in the supine position for at least 5 minutes. All results are recorded on the ‘Vital Signs Pre-Infusion’ or ‘Vital Signs Post Infusion’ eCRF pages.*

The baseline value is as described in Section 7.1. The arithmetic mean of all triplicate values is calculated for use in summary tables. Results are converted for summary tables as follows:

- Temperature: Results measured in Fahrenheit converted to Celsius as
  - $\text{Temperature (}^\circ\text{C)} = (\text{Temperature (}^\circ\text{F)} - 32) * 5/9$
- Weight: Results measured in pounds converted to kilograms as
  - $\text{Weight (kg)} = \text{Weight (lb)} / 2.205$
- Height: Results measured in inches converted to centimetre as
  - $\text{Height (cm)} = \text{Height (in)} * 2.54$

The change from baseline is calculated for vital signs with a continuous response at each scheduled post-baseline visit:

- $\text{Change from baseline} = \text{Scheduled Visit result (measured or derived)} - \text{Baseline value.}$

At each scheduled post-baseline visit each vital sign with a continuous response is derived as having a clinically notable change using the rules in Table 5.

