### 9.2 Study Population

#### 9.2.1 Inclusion Criteria

To be eligible, the patient must meet all of the following criteria:

1. Patients completed the double-blind period in the IEDAT-02-2015 trial and have completed the final (Visit 15/Month 12) efficacy assessments of IEDAT-02-2015 or discontinued the study during the COVID-19 pandemic
2. Patients tolerated the study medication without any evidence of steroid adverse events, or treatment - related severe/ serious adverse events.
3. Body weight > 15 kg.

4. The patient and his/her parent/caregiver (if below the age of consent), or a legal representative, has provided written informed consent to participate. If consent is provided solely by the caregiver in accordance with local regulations, the patient must provide assent to participate in the study.
5. Patient does not present safety contraindications for continuation of treatment, as determined by the Principal Investigator (PI) according to the procedures described below.

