### 6.3 Subgroup Definitions

Patients are grouped by their treatment group in the ATTeST study: EDS-EP Low Dose, EDS-EP High Dose, Non-switch Placebo, Visit 9 Low Dose, Visit 9 High Dose, Visit 12 EDS-EP Low Dose, and Visit 12 High Dose. All outputs contain columns to display these groups.

The following endpoints are also summarised by subgroups for Age (<10; ≥10 years) and Region (India; Europe, Australia, and Tunisia; United States):

- ICARS
- mICARS
- RmICARS
- CGI-C
- CGI-S
- EQ-5D-5L

Patients with a treatment gap of greater than 76 days between the ATTeST study and the OLE-IEDAT study are presented as a separate subgroup for outputs as outlined in Section 10.

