### 7.4.2 Demographic and Other Baseline Characteristics

#### Age

Age (years) is calculated at Baseline based on the date of informed consent as recorded on the 'Informed Consent' eCRF page and the date of birth as collected on the 'Demography' eCRF page as:

$$\text{INT}(\text{date of informed consent} - \text{date of birth})/365.25).$$

Where INT denotes the integer part of the calculation. In case of incomplete dates, missing days are set to 16th and missing months are set to June. If, as a result of this imputation, the age of the patient is 5 years, then the age is set to 6 years.

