**Table 5: Clinically Notable Values for Vital signs**

| Parameter                      | Unit             | Decrease                               | Increase                                  |
|--------------------------------|------------------|--|---|
| Systolic Blood Pressure (SBP)  | mmHg             | Value $\leq 90$ and $\geq 20$ Decrease | Value $\geq 180$ and $\geq 20$ Increase   |
| Diastolic Blood Pressure (DBP) | mmHg             | Value $\leq 50$ and $\geq 15$ Decrease | Value $\geq 105$ and $\geq 15$ Increase   |
| Sitting Pulse Rate             | bpm              | Value $\leq 50$ and $\geq 15$ Decrease | Value $\geq 120$ and $\geq 15$ Increase   |
| Weight                         | kg               | $\geq 7\%$ Decrease                    | $\geq 7\%$ Increase                       |
| Respiration Rate               | breaths/minute   | $< 12$                                 | $> 25$                                    |
| Temperature                    | $^\circ\text{C}$ | NA                                     | Value $\geq 38.3$ and $\geq 1.1$ Increase |
| Temperature                    | $^\circ\text{F}$ | NA                                     | Value $\geq 101$ and $\geq 2.0$ Increase  |

“Decrease” and “Increase” refer to change from baseline. Respiration Rate is based on recorded value only and not change from baseline.

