### 10.7.6 Vital Signs

All Vital Sign data are included in a listing for the SAF.

Vital Sign results and change from baseline are summarized by summary statistics on scheduled visits for the SAF. The absolute counts (n) and percentages (%) of patients with clinically notable findings are included in a separate summary for the SAF. The absolute counts (n) and percentages (%) of patients with at least one clinically notable change from baseline and summary statistics of the most extreme clinically notable increase and decrease from baseline are presented in separate summaries for the SAF.

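### Height, weight and BMI are summarised only as raw values and changes, and the 7% weight flag ignores age and elapsed time, so the planned tables do not show growth for age

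*SAP*

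**What the plan says.** **The flag.** SAP 7.4.8 (Vital Signs) states that at scheduled post-baseline visits "each vital sign with a continuous response is derived as having a clinically notable change using the rules in Table 5". The weight row of Table 5 is a 7% or greater decrease or increase. The table note says that these terms "refer to change from baseline", and baseline is the OLE-IEDAT baseline of SAP 7.1. The weight row has no age, sex or time condition. Table 5 has no row for height or BMI.

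**The summaries.** SAP 7.4.2 takes height, weight and BMI as recorded, or as the mean of triplicates. SAP 10.4.1 summarises them at baseline. SAP 10.7.6 summarises vital-sign results and changes at scheduled visits. It adds counts of "patients with clinically notable findings are included in a separate summary for the SAF", and separate summaries of "patients with at least one clinically notable change from baseline and summary statistics of the most extreme clinically notable increase and decrease from baseline".

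**Age.** SAP 6.3 states: "The following endpoints are also summarised by subgroups for Age". Its list holds ICARS, mICARS, RmICARS, CGI-C, CGI-S and EQ-5D-5L, and no vital sign. SAP 7.4.2 states: "Age (years) is calculated at Baseline based on the date of informed consent". The result is cut to whole years. For incomplete birth dates, "missing days are set to 16th and missing months are set to June".

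**Population and duration.** Protocol 9.2.1 requires "Body weight > 15 kg". The SAP's age categories start at 6 years. The protocol synopsis plans 12 months of treatment, extendable without a fixed end.

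**Related outputs.** BMD Z-scores are summarised with change from baseline (Protocol 13.8, SAP 10.7.10). Tanner stage is counted by visit (SAP 10.7.11). Stunted growth and weight gain are adverse events of special interest, found by manual review of reported events (SAP 7.4.8).

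**The concern.** Long-term safety is the primary objective, the drug is a steroid, and the SAP itself treats weight gain and stunted growth as potentially steroid-related. The study includes children from 6 years and has no concurrent control.

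A fixed percentage change from a fixed baseline means different things in a growing child and in an adult, and different things at 6 months and at 3 years. The increase flag mixes expected growth with any excess gain. The decrease flag needs actual weight loss, so slow growth or a standstill does not set it. Raw mean changes have the same difficulty, because each ATTeST group column pools all ages. If a treatment slowed growth, or added weight beyond growth, these tables would not readily show either.

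**Working it through.** The plan gives no figure to reproduce here; the study is descriptive and has no formal sample size. The finding rests on the text. The arithmetic below only illustrates how the weight rule behaves.

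**Inputs.** The 7% rule (SAP Table 5). An entry limit of 15 kg (Protocol 9.2.1). As an illustration, 29.1 kg, the mean weight in the phase II AT study (Protocol 7.1.3.1), which is not this trial's mean. Growth rates are assumptions, because the documents give none.

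**Step 1, gain needed for the increase flag.** 0.07 × 15 = 1.05 kg; 0.07 × 29.1 = 2.04 kg.

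**Step 2, average yearly gain that reaches the flag by a given time** (gain needed ÷ years).
- From 15 kg: 1.05 kg/year by 12 months, 0.53 by 24, 0.35 by 36.
- From 29.1 kg: 2.04, 1.02 and 0.68 kg/year.

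The yearly gain that sets the flag falls in proportion to follow-up time.

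**Step 3, months to the flag under an assumed steady gain** (12 × 0.07 × starting weight ÷ yearly gain).

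| Assumed gain (kg/year) | From 15 kg | From 29.1 kg |
|---|---|---|
| 0.5 | 25.2 | 48.9 |
| 1 | 12.6 | 24.4 |
| 2 | 6.3 | 12.2 |
| 3 | 4.2 | 8.1 |

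From 29.1 kg, gains of 0.5 to 2 kg/year are not flagged within the planned 12 months. The effect grows with extension beyond the first year and is largest in light patients.

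**Step 4, the lower side.** With zero gain the change is 0%, so the weight rule never fires. If expected growth is r per year, such a child lies 1 − 1/(1+r)^t below expected weight after t years. For assumed r of 5% and 10%:
- at 2 years, 1 − 1/1.1025 = 9.3% and 1 − 1/1.21 = 17.4%;
- at 4 years, 1 − 1/1.2155 = 17.7% and 1 − 1/1.4641 = 31.7%.

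The decrease flag fires only at a shortfall of 1 − 0.93/(1+r)^t. At 2 years that is 15.6% and 23.1%.

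**Step 5, whether another planned output fills the gap.** BMD Z-scores are age-referenced but concern bone. Tanner stage describes puberty, is tabulated as counts, and leaves out patients who have completed puberty. The special-interest events depend on someone reporting an event. The age subgroups exclude vital signs. None of these gives height, weight or BMI for age.

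**Step 6, accuracy of age for a z-score.** Whole-year age at consent is too coarse and does not advance with visits. Where birth month is missing, 16 June is 166 days after 1 January and 198 days before 31 December, so age can be wrong by up to 198 days, about 6.5 months.

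**The case against.** The best opposing case is that the plan already looks at steroid effects on growth in several ways. It analyses bone density by Z-score under a paediatric guideline. It uses Tanner staging, which Protocol 13.9 names for the effect of dexamethasone on physical development. It lists growth-related events of special interest and summarises raw height and weight by visit. The study is descriptive, so no test is invalidated. Height and weight are listed, so z-scores could be derived later. AT itself may affect development, so comparison with a reference population is confounded. Some columns are thin: about 60 placebo patients in ATTeST, one third switched at each step and split 1:1, gives 60/3/2 = 10 per switch group before dropout.

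Much of this stands as a limit on what z-scores can show. It does not supply the missing summary, and the BMD analysis shows that age-referencing is already accepted in this plan.

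A reader might infer more than the documents support:
- That growth is unexamined, or that nothing is age-referenced. The outputs just listed contradict this.
- That most increase flags will be growth. No growth rate or age mix is given, so the share cannot be computed.
- That the notable-value counts ignore visit. SAP 7.4.8 derives the flag per visit. SAP 10.7.6 does not state the layout of the counts, and the table shells that SAP 5.3 treats as specifications were not available. This is unknown, not missing.
- That follow-up reaches five years. An adverse-event interval ending at day 1824 does not establish that.

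**Conclusion.** The point holds as a cheap improvement to the safety analysis, not as an error in the plan. On the text, height, weight and BMI are never age-referenced, and the 7% weight rule carries no age or time term. In growing patients the increase flag becomes easier to reach by ordinary growth as follow-up lengthens, and zero gain is never flagged by weight.

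The size is fixed only in part. The threshold is 1.05 kg at the entry limit and 2.04 kg at the illustrative 29.1 kg. All times to the flag and all shortfalls from expected weight rest on assumed growth rates. Protocol Appendix 4, the ADaM specifications and the table shells were not available. The vital-sign flags are nevertheless derived from Table 5, which is shown in full.

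**What to change.** In SAP 7.4.8 and 10.7.6:

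- Keep the raw summaries and the 7% flag as they are.
- For patients under 18, add age- and sex-standardised z-scores for height, weight and BMI from one reference named in the SAP. State whether under 18 is judged at baseline or at the visit.
- Derive age at each visit from date of birth and visit date, not from whole-year age at consent.
- Summarise the z-scores by scheduled visit, with change from OLE-IEDAT baseline and, where the ATTeST datasets supply the values, from ATTeST baseline.
- State that in this group the 7% weight flag is read alongside the z-scores.

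**Cost.** SAP wording and a standard derivation from data already collected; no new visits or measurements. No clinical rule changes.

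**Downsides.** One reference must serve a multinational AT population. Stadiometer height may be unreliable or missing in wheelchair users, which affects height and BMI z-scores more than weight. Imputed birth dates can misstate age by up to about 6.5 months, so affected patients should be identifiable. Without a control group, a falling z-score cannot separate drug effect from disease.

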**Table 5: Clinically Notable Values for Vital signs**

| Parameter                      | Unit             | Decrease                               | Increase                                  |
|--------------------------------|------------------|--|---|
| Systolic Blood Pressure (SBP)  | mmHg             | Value $\leq 90$ and $\geq 20$ Decrease | Value $\geq 180$ and $\geq 20$ Increase   |
| Diastolic Blood Pressure (DBP) | mmHg             | Value $\leq 50$ and $\geq 15$ Decrease | Value $\geq 105$ and $\geq 15$ Increase   |
| Sitting Pulse Rate             | bpm              | Value $\leq 50$ and $\geq 15$ Decrease | Value $\geq 120$ and $\geq 15$ Increase   |
| Weight                         | kg               | $\geq 7\%$ Decrease                    | $\geq 7\%$ Increase                       |
| Respiration Rate               | breaths/minute   | $< 12$                                 | $> 25$                                    |
| Temperature                    | $^\circ\text{C}$ | NA                                     | Value $\geq 38.3$ and $\geq 1.1$ Increase |
| Temperature                    | $^\circ\text{F}$ | NA                                     | Value $\geq 101$ and $\geq 2.0$ Increase  |

“Decrease” and “Increase” refer to change from baseline. Respiration Rate is based on recorded value only and not change from baseline.

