#### Demographics and Disease Characteristics

The mean (SD) age of the AT patients was 11.2 (3.5) years, with 11 (50%) patients being males. All patients were Caucasian with a mean weight of 29.1 (9.5) kg and BMI of 15.6 (2.6). The average age of diagnosis of AT was 60.0 (35.2) months, with a mean age of symptom onset of 25.9 (17.5) months. The mean baseline scores for the ICARS and VABS were 50.6 (12.8) and 5.5 (2.0), respectively. Mean baseline scores on the sub-scales of the ICARS were as follows: posture/gait disturbance – 20.9 (7.1); kinetic function – 23.1 (6.2); speech disorders – 3.5 (1.4); and oculomotor disorders – 3.2 (1.0). Two patients were on inhalational steroids at screening, and these medications were discontinued.

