### 16.2 Statistical Methods

#### 16.2.1 *Sample Size*

There is no formal sample size calculation, as the sample size is dependent on the number of patients who complete the double-blind extension study (Protocol IEDAT-02-2015), express the desire to continue treatment with the investigational drug, and meet the selection criteria defined in [Section 9.2](#) of the Study IEDAT-03 protocol. It is expected that a maximum of 150 patients will enter this open-label extension.

The following analysis sets will be used:

- 1) *Efficacy Population (EP)*: All patients who enter study IEDAT-03, have a baseline efficacy assessment in study IEDAT-03, and who received at least one dose of study medication and had at least one post-baseline efficacy assessment of the primary efficacy variable in this extension study.
- 2) *Safety Population (SP)*: All subjects who receive a dose of study medication, and have at least one post-dose safety assessment will be included in the safety analyses.

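### The blood-pressure increase flag in SAP Table 5 will rarely fire in this cohort, so a near-zero count of notable increases should not be read as absence of a rise

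*SAP*

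**What the plan says.** SAP section 7.4.8 (Vital Signs) says that at each scheduled post-baseline visit every continuous vital sign is "derived as having a clinically notable change using the rules in Table 5". For increases, the systolic rule is "Value $\geq 180$ and $\geq 20$ Increase" and the diastolic rule is "Value $\geq 105$ and $\geq 15$ Increase". The note under the table says that the increases and decreases "refer to change from baseline". One set of limits serves all ages.

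SAP section 10.7.6 builds its patient-level outputs on this flag: counts of patients with notable findings, counts of patients with at least one notable change, and a summary of the most extreme notable rise and fall. Separately, "Vital Sign results and change from baseline are summarized by summary statistics on scheduled visits for the SAF", and all vital signs are listed. Vital-sign changes are part of the primary safety endpoint (SAP section 3.4).

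The age distribution of this extension is not given. The phase II ataxia telangiectasia study is the nearest guide: "The mean (SD) age of the AT patients was 11.2 (3.5) years" (Protocol section 7.1.3.1). Protocol section 7.1.3 adds that one of its 22 patients was 19 at inclusion. The SAP uses age classes of 6 to under 10 and 10 or over, a children's C-SSRS for those under 12 at baseline, and Tanner staging.

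**The concern.** The two conditions are joined by *and*, and the absolute limit is far above the pressures one would expect in children and adolescents. For nearly all such patients the rise condition has no effect, and the flag becomes a test of whether pressure reached 180 or 105 mmHg.

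The study drug is a corticosteroid and long-term safety is the primary objective. A row showing no or almost no notable increases could be taken as reassurance when it mainly reflects where the limit was set. The listed steroid-related adverse events of special interest (SAP section 7.4.8) do not include raised blood pressure, so that list does not supply the missing patient count.

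**Working it through.** The plan states no flag rate and no power figure for this point ("There is no formal sample size calculation"), so there is nothing to reproduce. The check is of the rule itself.

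**Inputs.** From SAP Table 5: limit T = 180 systolic, 105 diastolic; minimum rise d = 20 and 15 mmHg. From Protocol section 16.2.1: "It is expected that a maximum of 150 patients will enter this open-label extension". Assumed, because the documents give no blood pressures: resting values of 90-120/50-80 mmHg; for the probability check, systolic means of 95-125 with SD 10-15, diastolic means of 55-75 with SD 8-12, and an SD of change of 8-12 mmHg.

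**Step 1: rise needed.** With baseline B, the rise needed is max(d, T - B). The rise condition decides only when B is at least T - d, which is 180 - 20 = 160 systolic and 105 - 15 = 90 diastolic.

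| | Baseline (mmHg) | Rise needed (mmHg) |
|---|---|---|
| Systolic | 90 | 90 |
| Systolic | 105 | 75 |
| Systolic | 120 | 60 |
| Diastolic | 50 | 55 |
| Diastolic | 65 | 40 |
| Diastolic | 80 | 25 |

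The decrease rule behaves differently. From a systolic baseline of 110, a fall of 20 mmHg reaches its limit of 90, while an increase flag from the same baseline needs 70 mmHg.

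**Step 2: flag rate at one visit after a real shift.** Upper bound = P(value at least T) under a normal distribution with the mean moved by the shift. It is an upper bound because the rise condition is ignored.

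- Systolic, shift +20, mean 95, SD 10: z = (180 - 115)/10 = 6.5, or 4 in 10^11.
- Systolic, shift +20, mean 115, SD 15: z = (180 - 135)/15 = 3.0, or 0.14%. In 150 patients that is 0.2 patients.
- Systolic, shift +20, mean 125, SD 15: z = (180 - 145)/15 = 2.33, or 1.0%.
- Diastolic, shift +15, mean 55, SD 8: z = (105 - 70)/8 = 4.38, or 6 in a million.
- Diastolic, shift +15, mean 65, SD 12: z = (105 - 80)/12 = 2.08, or 1.9%.
- Diastolic, shift +15, mean 75, SD 8 to 12: z = 1.88 to 1.25, or 3% to 11%.

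If the mean shift equals d, half the patients (75 of 150) would meet the rise condition alone at that visit.

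**Step 3: share under 18.** Using the phase II ages and a normal approximation, (18 - 11.2)/3.5 = 1.94, or 97%. If this cohort is three years older on average, (18 - 14.2)/3.5 = 1.09, or 86%.

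**Step 4: chance flags in a change-only count.** With no true change, at one visit 1 - Φ(20/SD) gives 0.6% to 4.8% systolic and 1 - Φ(15/SD) gives 3.0% to 10.6% diastolic, for SD 8 to 12. Over 12 post-baseline visits sharing one baseline reading, with independent errors of SD s = SD/√2 at each visit, P(at least one) = 1 - ∫φ(z)Φ((c + sz)/s)^12 dz, where c is 20 or 15. This gives 5% to 26% systolic and 19% to 45% diastolic.

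**The case against.** The strongest reply is that this flag is only one output among several. The by-visit summaries give mean, SD, quartiles, minimum and maximum of the change (SAP sections 8.1 and 10.7.6), so both a general shift and one patient's large rise would appear there, and every value is listed. Investigators can report raised pressure as an adverse event, and the DSMB receives clinically significant vital signs. All of this stands. A reader might infer that blood-pressure rises would go unseen in this study; the documents do not support that.

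A reader might also infer that the rule can flag nobody. That goes too far. A patient already near 160/90, or one with an extreme rise, would be flagged, and Step 2 allows a diastolic rate of several percent at a mean of 75 mmHg.

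Nor does Table 5 call a 20 or 15 mmHg rise notable on its own. Those figures are the minimum change required alongside an extreme value. They are convenient cut points for a descriptive count, but they are not a competing standard within the SAP.

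Lastly, Protocol section 13.2 places the guidelines for notable vital signs in Appendix 4, which is not in the available text. Table 5 may follow it, and any rationale there cannot be checked.

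**Conclusion.** The point holds as a low-priority reporting gap. The 20/15 mmHg conditions decide the flag only from a baseline of 160/90 mmHg or more. Over the assumed resting range, a flag needs three to four and a half times the systolic minimum rise (60-90 against 20) and about 1.7 to 3.7 times the diastolic one (25-55 against 15). A near-zero count of notable increases in Table 14.3.3-2.2 is therefore not evidence that pressure does not rise. Moderate rises in a minority of patients would show only in the listings and in the spread of the by-visit summaries, with no patient count.

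This rests on two things the documents do not state: the baseline pressures, which are assumed, and a mainly paediatric cohort, which is inferred from the age classes, the Tanner and children's C-SSRS provisions, and the phase II ages. The documents also give no size for a steroid-related pressure rise, so nothing here says that one is expected or how large it would be.

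**What to change.** Keep the Table 5 flags unchanged. Add descriptive rows to Table 14.3.3-2.2 counting patients whose change from baseline is at least 20 mmHg systolic or at least 15 mmHg diastolic, by visit and at any visit. State whether the pre- or post-infusion reading is used. Show falls of the same size beside the rises, as a rough guide to how many flags come from measurement noise. Add a footnote that a low count under the Table 5 increase rule does not exclude smaller rises.

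Optionally, add (without replacing the 180/105 rule) a summary referenced to age, sex and height for patients under 18, naming the paediatric reference in the SAP.

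The added rows need a short derivation and no new data. The optional summary also uses data already collected but depends on an external reference that has to be chosen and programmed. The main downside is chance flags, which accumulate over visits (Step 4). With no concurrent control arm, the rows should be labelled descriptive only. They also cannot show a rise that took place in the preceding study, because change is measured from the extension baseline.
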